	
Device Trial: Day 0 (≤ 14 days post Baseline Visit)                  At Day 0, subjects will be implanted with two percutaneous leads per labeling. Subjects who have leads spanning the T9/T10 disc space will continue in the study. In the recovery room, subjects who have electrodes over the T9/T10 disc space will be programmed with 1 HD programming configuration.
 
Device Trial Day 2: (2 – 4 days after Device Trial Day 0)                  The effectiveness of the stimulation parameters programmed at Day 0 will be assessed for 2 days. If a subject has ≥ 50% reduction in pain, they will have their trial leads explanted and proceed to implant. If a subject does not have ≥ 50% pain relief, they will be reprogrammed to the second HD group and return for a Day 4 Visit.
 
Device Trial Day 4, if necessary: (2 – 4 days after Day 2 Visit)                  The effectiveness of the stimulation parameters programmed at Day 2 will be assessed for 2 days. If a subject has ≥ 50% reduction in pain, they will have their trial leads explanted and proceed to implant. If a subject does not have ≥ 50% pain relief, they will be reprogrammed using any on-label parameters (physician preference) and return for a Day 6 Visit
 
Device Trial Day 6, if necessary: (2 – 4 days after Day 4 Visit; no later than Day 10)                  Subjects will return to the clinic a minimum of two days later to assess the effectiveness of the physician preference stimulation parameters programmed at Day 4 and have their trial leads explanted. These subjects will then be exited from the study.
 
Implant (≤ 30 days post end of device trial)                  Subjects who were HD responders during the device trial and who met all eligibility criteria will be implanted with a RestoreSensor SureScan MRI or Intellis AdaptiveStim neurostimulation system. Subjects will be implanted with two compact percutaneous leads per labeling. Subjects who have leads spanning the T9/T10 disc space will continue in the study. The stimulator will be “OFF” when the subject leaves this visit.
 
Device Activation Visit (9 – 16 days post implant) The Device Activation Visit will take place 9 – 16 days after implant, pending wound healing. The stimulator will be turned “ON” at this visit and the programming that was successful for the trial will be programmed for that subject.
 
Follow-up Visits (2 weeks, 4 weeks, 6 weeks ± 3 days and 3, 6, and 12 Months ± 15 days post Device Activation)                  Visits will occur at weeks 2, 4 and 6 and months 3, 6 and 12 post device activation. EQ-5D-5L, ODI, PGIC, and SSA will be assessed at 3-, 6- and 12-Months. The VAS

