**Table 2. Protocol Visit Windows**

Visit	Visit ranges
Baseline Visit	NA
Device Trial Day 0	≤ 14 days after Baseline visit
Device Trial Day 2	2 + 2 days after Device Trial Day 0
Device Trial Day 4, if necessary	2 + 2 days after Device Trial Day 2
Device Trial Day 6, if necessary	Must occur 2 days after Device Trial Day 4 Visit and before or on Device Trial Day 10
Implant Visit	≤ 30 days after end of device trial
Device Activation Visit ( Day 0 )	9 -16 days after implant; pending wound healing
1-Week Telephone Call	7 ± 3 days after Day 0
2-Week Clinic Visit	14 days ± 3 days after Day 0
3-Week Telephone Call	21 ± 3 days after Day 0
4-Week Clinic Visit	28 days ± 3 days after Day 0
5-Week Telephone Call	35 ± 3 days after Day 0
6-Week Clinic Visit	42 days ± 3 days after Day 0
7-Week Telephone Call	49 ± 3 days after Day 0
8-Week Telephone Call	56 days ± 3 days after Day 0
9-Week Telephone Call	63 ± 3 days after Day 0
10-Week Telephone Call	70 days ± 3 days after Day 0
11-Week Telephone Call	77 ± 3 days after Day 0

Visit	Visit ranges
3-Month Clinic Visit	90 days ± 10 days after Day 0
3.5-Month Telephone Call	105 days ± 15 days after Day 0
4.5-Month Telephone Call	135 days ± 15 days after Day 0
5.5-Month Telephone Call*	165 days ± 15 days after Day 0
6-Month Clinic Visit	180 days ± 15 days after Day 0
6.5-Month Telephone Call*	195 days ± 15 days after Day 0
7.5-Month Telephone Call	225 days ± 15 days after Day 0
8.5 Month Telephone Call	255 days ± 15 days after Day 0
9.5-Month Telephone Call	285 days ± 15 days after Day 0
10.5-Month Telephone Call	315 days ± 15 days after Day 0
11.5-Month Telephone Call*	345 days ± 15 days after Day 0
12-Month/Final Clinic Visit	360 days ± 15 days after Day 0

\* For instances where the monthly telephone call window overlaps the clinic visit window, if the clinic visit occurs within the telephone call window, the telephone call is not required.

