## 9.19. Subject Withdrawal or Discontinuation

A subject has the right to withdraw from the study at any time and for any reason without prejudice to his/her future medical care by the principal investigator or institution. Subjects will be provided standard medical care by their physician after their study participation ends.

The study sample size accounts for expected attrition, thus subjects that discontinue after implant will not be replaced.

If a subject is withdrawn from the study, the reason for withdrawal shall be recorded on a study exit eCRF and in the subject's medical record. Examples of reasons for study discontinuation include, but are not limited to, the following:

- Eligibility criteria not met
- Pregnancy
- Failure to follow study requirements
- Subject death
- Subject lost to follow-up (LTFU)
- Subject voluntarily withdraws from the study
- Adverse events
- Normal study completion

A study exit eCRF will be completed for any enrolled subject who permanently discontinues from the study or completes the protocol-required study follow-up and has completed the study.

In the case that the subject is determined to be lost to follow-up, details of a minimum of three attempts and the method of attempt (e.g., two by phone and one by certified letter) to contact the subject must be recorded in the subject's medical records. In addition, requirements set forth by the governing IRB/EC must be followed.

The investigator should make all attempts to conduct a discontinuation visit prior to subject withdrawal if the subject is withdrawn after the Device Activation Visit and outside of a protocol-required visit. All eCRFs should be completed for visits that occurred prior to the subject’s withdrawal. In addition, regardless of when the discontinuation occurs, the subject should be asked to complete all 12-Month/Final Visit procedures, if the subject is willing, in order to obtain final assessments for the study. A study exit eCRF must also be completed.

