**Table 5. Data collection requirements for subject withdrawal**

Time of Early Withdrawal	Procedures Required
Prior to Device Activation	Complete appropriate visit eCRFs based on the visits completed (e.g. Baseline, Device Trial etc.) prior to discontinuation and the study exit eCRF.
After Device Activation and prior to the 12-Month/Final Visit	Complete all appropriate visit eCRFs based on visits completed prior to the discontinuation, the 12-Month/Final Visit eCRF (if subject is willing), and study exit eCRF.

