## 11.3. Recording of Adverse Events

In this study, only device-, therapy- and procedure-related adverse events (AEs) and device deficiencies that occur from enrollment through subject discontinuation from the study will be collected. Adverse event and device deficiency information will be reported to Medtronic on an adverse event or device deficiency eCRF, one for each AE and/or device deficiency.

It is the responsibility of the investigator to identify the occurrence of device-, therapy- or procedure-related adverse events and device deficiencies and to ensure all required information is accurately recorded on the eCRF. Refer to the applicable eCRF for the information to be reported for each adverse event and device deficiency.

For adverse events that require immediate reporting, initial reporting to Medtronic may be done by phone, or e-mail, or on the eCRF by completing as much information as is available. The adverse event eCRF must be completed as soon as possible.

In case the investigator requires information from the sponsor in an emergency situation, the investigator can contact Medtronic using the contact details provided in the synopsis and Section 11.7.

The clinical course of each adverse event must be followed until the adverse event is resolved, the subject is in a stable condition, or until the subject discontinues from the study. "Ongoing" adverse events and device deficiencies must be assessed at each study visit. The adverse event eCRF should be updated when there is a change to the information provided on the form (e.g. change in intervention, outcome, relatedness, etc.).

At the last scheduled visit, the investigator will instruct the subject to provide an update on the status of any ongoing events and report any adverse event or issue with the device that they believe might be related to participation in the study.

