**Table 6: Expected Surgical Adverse Events and Durations**

Event description	Time frame after the surgical procedure
Anesthesia-related nausea/vomiting	24 hours
Mild to moderate pain at surgical site	7 days
Low-grade fever (<100°F or < 37.8°C)	48 hours
Mild to moderate bruising / ecchymosis	7 days
Pocket site / incisional pain	14 days
Seroma	72 hours
Sleep problems (insomnia)	72 hours

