7.10.1.2. Trialing Events

Events that have an onset date on or after the Device Trial (Day 0) Visit and either through the Study Exit date or prior to the Implant Visit (whichever date is earlier) will be summarized as Trialing Events. The denominator for percent of subjects who experienced the event will be all subjects in the Tried Analysis Set.

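### Device-trial non-responders are exited when their leads come out, but share one Trialing Events percentage with responders observed for up to 30 more days, so post-explant events are undercounted

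*Protocol*

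**What the plan says.** **Exit of non-responders.** A subject without sufficient relief on HD settings by the Day 4 Visit is reprogrammed to physician-preference settings and returns for the Day 6 Visit, "no later than Day 10". There these subjects "have their trial leads explanted. These subjects will then be exited from the study" (Protocol, Synopsis). Protocol 8.2 classes them as screen fails.

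**End of collection.** Protocol 11.3 collects related adverse events and device deficiencies from enrollment until the subject discontinues. A known event is followed until it resolves, "the subject is in a stable condition, or until the subject discontinues from the study". The visit list in 9.1 and Tables 2 and 4 show no visit or call for these subjects after explant. For withdrawal before activation, Table 5 asks only for the forms of visits completed "prior to discontinuation and the study exit eCRF".

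**Responders.** They remain in the study until the Implant Visit, which Table 2 places "≤ 30 days after end of device trial". The heading of Protocol 9.4 counts those days from trial lead explant.

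**Reporting.** SAP 7.10.1.2 counts events with onset from Trial Day 0 and "either through the Study Exit date or prior to the Implant Visit (whichever date is earlier". The denominator is the whole Trialed Analysis Set. The Protocol and SAP define that set differently (leads at T9/T10 and programmed, against any Day 0 Visit), but HD non-responders belong to it under both. SAP 7.7 measures trial exposure from Day 0 to lead explant.

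**The concern.** Length of observation in the Trialing phase depends on the trial outcome, and the denominator takes no account of this. A responder who develops an infection in the weeks after the trial leads come out is still in the study, and the event counts. A non-responder with the same infection has already been exited, and the event falls outside collection, yet the subject stays in the denominator.

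The reporting rule for expected surgical events adds to this. Under Protocol 11.6 and Table 6, such an event becomes reportable only if it worsens or lasts beyond a stated period, the longest being 14 days for "Pocket site / incisional pain". A subject exited at explant cannot be seen to pass a period that starts at explant.

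Safety characterization from enrollment to exit is a stated aim (Protocol 5.1.2, SAP 4.2). What is at stake is whether the Trialing percentage can be read as the risk of going through a device trial. It cannot be compared with another study, or across sites with different trial success, without knowing the failure share.

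**Working it through.** The plan gives no figure for this effect, so there is none to reproduce. The check is visit-window arithmetic followed by a dilution formula.

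**Step 1. Timing of explant** (Protocol, Synopsis and Table 2).
- Day 2 Visit: 2 to 2 + 2 = trial day 2 to 4.
- Day 4 Visit: 2 + 2 to 4 + 4 = trial day 4 to 8.
- Day 6 Visit: 4 + 2 to 8 + 2 = trial day 6 to 10, which agrees with the Day 10 cap.

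**Step 2. Exposure as reported, and observation as planned.**

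| Group | SAP 7.7 trial exposure (days) | Planned observation after explant (days) | Trialing window in total (days) |
|---|---|---|---|
| Responder at Day 2 | 2 to 4 | up to 30 | up to 4 + 30 = 34 |
| Responder at Day 4 | 4 to 8 | up to 30 | up to 8 + 30 = 38 |
| HD non-responder | 6 to 10 | 0 | 6 to 10 |

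The exposure summary therefore shows non-responders with the longer time. That is correct for time with leads in place and the reverse of the order for time under observation.

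**Step 3. Dilution of post-explant events.** Let *r* be the percentage of trialed subjects with a related event after explant, taken as equal in both groups, and *f* the share of trialed subjects exited at explant. If responders are observed for the whole risk period:

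reported = *r* × (1 − *f*), so the relative shortfall is *f*.

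The documents do not give *f*. Protocol 13.3.4 enrolls up to 215 to have 100 reach 3 months. On those planning figures *f* cannot exceed 115/215 = 53.5%, reached only if everyone lost were a trial failure. I take 10% to 45% as the working range and 2% and 5% for *r*; all are assumptions.

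**Step 4. Dilution of the whole Trialing percentage.** Let *a* be the percentage of subjects with an event before explant, when both groups are observed, and let *r* now count other subjects only. Then reported = *a* + *r* × (1 − *f*), against a true *a* + *r*. With *a* = 8%, also assumed:

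| *f* | Post-explant, *r* = 2% | Post-explant, *r* = 5% | Whole, true 8 + 2 = 10% | Whole, true 8 + 5 = 13% |
|---|---|---|---|---|
| 10% | 1.8% | 4.5% | 9.8% (2% low) | 12.5% (3.8% low) |
| 30% | 1.4% | 3.5% | 9.4% (6% low) | 11.5% (11.5% low) |
| 45% | 1.1% | 2.75% | 9.1% (9% low) | 10.75% (17.3% low) |

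**Step 5. Table 6 periods for a subject exited on day 6 to 10.** Counted from lead placement on Day 0, the 24-, 48- and 72-hour periods all end before exit, the 7-day periods end before exit only if exit is after Day 7, and the 14-day period never does, since 10 < 14. Counted from explant, none ends before exit.

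**The case against.** The case on the other side has real force in several places.

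- **Zero is planned follow-up, not a proven fact.** The Synopsis sets no date for the exit form, and the detailed Day 6 text in Protocol 9.3 is redacted. A site could leave a short gap. This stands as a limit, although no visible visit list or table contains a later contact.
- **The responders' 30 days are a maximum, and passive.** Nothing is scheduled between explant and the Implant Visit. This stands, but events are collected at that visit, so onsets in the interval can be recorded.
- **Many named risks belong to lead placement.** Protocol 10.1 ties hemorrhage and hematoma to placing the lead, and non-responders are watched longer with leads in place (6 to 10 days against 2 to 8). The documents do not say that explant starts a new Table 6 period. A reader might infer that no post-explant event in these subjects could ever become reportable. That goes too far: it depends on how the clock is read, and the shorter periods counted from placement end before exit.
- **The SAP already shows a good deal.** SAP 7.1.1 gives counts by stage and trial success by visit, and SAP 7.10.1 lists every event. This helps a reader estimate the failure share, but listings cannot show events that were never collected.
- **Section 9.19 offers a closing assessment.** It says "regardless of when the discontinuation occurs, the subject should be asked to complete all 12-Month/Final Visit procedures". That assessment takes place at exit, so it adds no time after explant, and Table 5 asks for the final-visit form only after activation. The mismatch needs reconciling but does not bear on the undercount.
- **The stakes are modest.** This is an on-label post-market study, subjects return to standard care, and the percentage is descriptive with no test attached. This stands and limits the weight of the point.

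**Conclusion.** On the visible text, observation after trial lead explant depends on trial outcome, one denominator covers both groups, and the planned exposure summary does not reveal it. Post-explant events are undercounted by the share of trialed subjects exited at explant: 10% to 45% over the assumed range, given equal risk in both groups and responders observed throughout the risk period. The direction follows from the design; the size rests on a share that the documents do not give.

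Three stronger readings are tempting and not supported:
- A reader might apply the 10% to 45% to the whole Trialing percentage. That percentage includes events before explant, when non-responders are observed, so the shortfall is smaller: 2% to 17% in the illustration above.
- A reader might infer that subjects can leave at permanent implant with a new system and no follow-up. This would rest on one Synopsis sentence about lead position, while the body of Protocol 9.4 is redacted.
- A reader might ask for follow-up days on implanted subjects who never reach activation. SAP 7.7 already provides them by substituting the study exit date.

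The effect is confined to descriptive Trialing-phase safety percentages. Efficacy and post-activation event tables use the Treated Analysis Set and are unaffected. The point is worth acting on because the correction is cheap.

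**What to change.** 1. **SAP 7.10.1.2.** Report Trialing Events in two parts: Day 0 through trial lead explant, with all trialed subjects as denominator; and after explant until Implant or study exit, with only subjects still under follow-up as denominator. Show observation days for each part. Events with onset on the explant date belong to the first part. The cost is SAP wording and one more table, using dates that the SAP already calls for.

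2. **Protocol exit procedure.** For subjects exited at trial lead explant, complete the study exit eCRF only after one adverse-event and device-deficiency telephone call, made once the longest Table 6 period (14 days) has passed since explant. State whether explant starts a Table 6 period. The call cuts the maximum difference in post-explant observation from 30 days to 30 − 14 = 16, and the observation days in item 1 show what remains. The cost is one call per early exit, a CIP amendment, and a slightly higher reported event rate.

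3. **Separately,** reconcile Protocol 9.19 with Table 5 on whether a subject who leaves before activation is asked for closing assessments. This is a wording correction and adds no follow-up after explant.

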## 4. Introduction

### 4.1. Background

Spinal Cord Stimulation (SCS) was first tested for the management of chronic intractable pain of the trunk and/or limbs in 1967. The device system used today consists of one or more epidural leads and a subcutaneously implanted neurostimulator. The energy delivered from the electrodes on the epidural lead modulates pain signals in the nervous system. The neurostimulator generates electrical pulses that are delivered to the dorsal columns of the spinal cord based on lead location and can be controlled by adjusting the programming parameters of amplitude, frequency, and pulse width. Because the tactile sensory neurons in the dorsal columns are stimulated with SCS, paresthesias or a tingling feeling from the treatment can be felt during stimulation.

Two branded types of stimulation, HF10™ and BurstDR™, have recently come on the SCS market. HF10 therapy delivers SCS therapy at a frequency of 10 kHz, which is significantly higher than other

commercial SCS devices with rates between 2 and 1200 Hz. Due to the high frequency used, the HF10 pulse width is typically around 30  $\mu$ sec. In contrast, BurstDR is delivered in a series of five pulses at 500 Hz, delivered at a 40-Hz rate. Pulse width is typically set at 1000  $\mu$ sec. Both of these programming algorithms deliver a higher dose of energy than conventional stimulation by increasing the parameters of frequency and/or pulse width. A “dose” of therapy can be calculated and presented as charge per second in micro-Coulombs ( $\mu$ C/s). In fact, the idea of higher energy delivery and energy/sec was reported as a possible explanation for the effects of BurstDR. Other programming parameters may also result in “high dose” (HD) stimulation. High dose contrasts with low dose (LD) therapy, which typically uses lower energy and frequencies between 30-100 Hz. Table 1 describes an example of parameters of HD stimulation.

**Table 1 SCS Dose**

Parameter	Medtronic Device Range	Description	Conventional	High Dose
Dose	Variable, based on settings	A product of pulse width, frequency, and current.  Reported in micro Coulombs per second ( $\mu$ C/sec), also referred to as Charge per second.	50 Hz, 400 $\mu$ sec, 4 mA = 80 $\mu$ C/sec	1000 Hz, 90 $\mu$ sec, 4 mA = 360 $\mu$ C/sec

SCS therapy relies on the delivery of energy to a specified stimulation spinal cord target. Conventional stimulation has targeted any area of the dorsal columns that result in a comfortable paresthesia perception over the painful area. HF10 therapy simplified SCS therapy by staggering two epidural leads along the midline from T8 to T11. The typical starting target for HF10 therapy is a bipole at the T9-T10 disc space. This is in accord with a study by Barolat et al. (1993), who determined that targeting the T9-T10 implanted “strictly midline” was the “best location” for SCS to treat low back pain without stimulation of the chest or abdominal wall. Barolat (2001) used conventional stimulation parameters at T9-T10 in which 68.8% of patients reported fair to excellent pain relief after 1 year of stimulation. In a recent study of HF10, the investigators placed two leads over the T9-T10 intervertebral space and reported that 84.5% of HF10 subjects were back pain responders, reporting greater than 50% pain relief.

While the patient outcomes with these stimulation parameters and location is promising, additional clinical research is needed to understand the amount of energy and the specific stimulation target that will result in the best patient outcomes.

## 4.2. Purpose

The purpose of this study is to evaluate the efficacy of spinal cord stimulation (SCS) therapy using HD stimulation parameters while targeting a specific anatomical location.

## 4.3. Regulatory Study Classification

This on-label, post-market clinical study using the RestoreSensor SureScan MRI and Intellis AdaptiveStim Neurostimulation Systems, FDA-approved, CE-marked, or licensed/market released devices, will be conducted in up to 30 sites and approximately 215 subjects with chronic, intractable pain of the back and legs may be enrolled globally. The study will be conducted in accordance with this protocol, the ethical principles that have their origin in the Declaration of Helsinki, all applicable regulatory requirements (In the US: 21 Code of Federal Regulations [CFR] §50 Protection of Human Subjects, and 21CFR§56 Institutional Review Board [IRB], 21CFR§803 Medical Device Reporting), and International Conference on Harmonization (ICH GCP E6). Regulatory requirements applicable to individual countries outside the US will be included in geography-specific addenda. This study will be posted on ClinicalTrials.gov as part of Medtronic's commitment to full disclosure for ongoing studies that meet the requirements for public posting.

Documentation for this study will be produced and maintained to ensure that a complete history of the study exists. Documents created for this study, including all versions of original documents, will be identifiable and appropriately stored to assure control and traceability of data related to this study.

